#### **6.1.1. Administration**

Participants will swallow the investigational product whole, and will not manipulate or chew the investigational product prior to swallowing and taking the capsules with a glass of water. Participants will be instructed to dose at a consistent time of day. Participants will be instructed to start taking their medication each day in the morning (AM dosing); however, it is permitted for participants to take his/her medication in the afternoon or evening prior to a clinic visit (eg, the Month 6 visit) when the timing of PK sample collection is prohibitive for adherence with AM dosing. Participants should not take an extra dose of medication in the event that a dose from a previous day is missed and should resume dosing capsules per day from an individual row on the study medication at the next planned dosing time. Similarly, if multiple doses are missed in succession, the participant should resume dosing at the next planned dosing time without taking additional doses to make up for those doses that were missed. Instructions on dosing are provided on the Participant Daily Dosing Diary.

At the end of each visit, sites will instruct participants, in writing on the front of the Participant Daily Dosing Diary, when to take their medication prior to their next study visit. This is especially important if the next visit has a collection of blood sample(s) for PK analysis.

Knowing the actual time of dosing is essential for appropriate analysis of samples for TTR stabilization, TTR concentration, and for tafamidis pharmacokinetic measurements. On the day of the study visit, participants will write the actual time that they took their medication in the Participant Daily Dosing Diary and the site staff will record this dosing time in the case report form (CRF).

On Day 1 (Baseline Visit), participants will be instructed to take their first daily dose of 61 mg tafamidis, after the completion of the baseline procedures and to continue dosing capsules each day in the morning (AM dosing) until the next study visit of Month 1 visit. At the end of the clinic visit, the participants will be reminded to take their medication in the clinic, rather than at home, on the day of the next visit of Month 1, as indicated on the Participant Daily Dosing Diary.

On the day of the Month 1 study visit, participants will NOT take their study medication at home prior to the clinic visit. Study medication on the day of the Month 1 visit will be taken in the clinic when instructed by clinic staff, in order to accurately and conveniently time the tafamidis concentration blood sample, which is to be collected pre-dose as well as 3 hours ( $\pm 1.5$  hours) after the actual time of dosing. The actual time of dosing will be recorded by the

study site personnel. Study site personnel will also record in the CRF the time of dosing on the day before the Month 1 visit as reported by the participant.

During Month 3 visit (Telephone visit), schedule the next appointment and participant will be instructed to take their medication **at home** prior to the next clinic visit as indicated on the Participant Daily Dosing Diary. Visit scheduling and dosing time instructions for participants must consider that the tafamidis concentration sample is to be collected 7 hours ( $\pm 2.5$  hours) after dosing. It should be noted that the participants are permitted to take the medication prior to the Month 6 visit in the afternoon or evening on the day prior to Month 6 visit if necessary to adhere to the PK sampling schedule. Participants will be instructed to accurately record on the Participant Daily Dosing Diary the actual time at which they took their prior 2 doses of medication taken at home prior to the Month 6 visit. The participant will be reminded to return to the clinic with all dispensed study medication.

For Month 6 visit, it should be noted that dosing should take place 7 hours ( $\pm 2.5$  hours) prior to the timing of PK sample. On the day prior to Month 6 visit, participants are permitted to take their usual AM dose and then take the next day's dose in the afternoon or evening if necessary to adhere to the PK sampling schedule. Participants will take their scheduled dose at home prior to the clinic visit (either in afternoon or evening of the day prior to this visit day, or in AM of this visit day) and record the actual time of dosing on their Participant Subject Daily Dosing Diary. Study site personnel will record in the CRF the time of the prior 2 doses of medication taken at home prior to the Month 6 visit as reported by the participant on their Participant Daily Dosing Diary.

During Month 9 visit (Telephone visit), schedule the next appointment and participant will be instructed to take their medication in the clinic, rather than at home, on the day of the next visit of Month 12. A Participant Daily Dosing Diary stating the date and time of the next visit of Month 12 will be issued to the participant. Participants will be instructed to accurately record on the Participant Daily Dosing Diary the actual time at which they took their dose of medication at home on the day before the Month 12 visit or End of Treatment visit. The participant will be reminded to return to the clinic with all dispensed study medication.

On the day of the Month 12 study visit, participants will **NOT** take their study medication at home prior to the Month 12 clinic visit. Study medication on the day of the Month 12 visit will be taken in the clinic in order to accurately and conveniently time the tafamidis concentration blood sample, which is to be 1 hour ( $\pm 30$  minutes) after the actual time of dosing. The actual time of dosing will be recorded by the study site personnel. Study site personnel will record in the CRF the time of dosing on the day before the Month 12 visit as recorded by the participant on their Participant Daily Dosing Diary.

In the event that participants experience adverse events that may be associated with the tolerability of treatment with tafamidis that may impact dosing adherence, they should return to the clinic with their medication. If the investigator assesses that the tolerability issue is persistent and anticipated to impact dosing adherence and that the participant's safety is not

compromised by continuing treatment, the site has the option to discontinue dosing for this participant and to terminate study participation.

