Documentation of vital status		X	X	X	X	X	X	
Record time of dosing		X	X		X		X	
Record dosing adherence			X		X		X	
Dispense investigational drugs		X	X		X			

- Visits, if applicable, are typically defined with respect to the Baseline visit and in accordance with expectations on the standard of care and/or required procedures for the study.
- Systolic and diastolic blood pressure (semisupine at least 5 minutes prior to assessment), pulse rate, respiratory rate and body temperature
- Biopsy or radionuclide bone scintigraphy (99mTc-PYP) for amyloid documentation must be performed at Screening or have been performed and documented within 5 years of enrollment. If greater than 5 years, biopsy or radionuclide bone scintigraphy (99mTc-PYP) must be repeated at the investigative site.
- Refer to [Appendix 4](#) for Contraceptive Guidance and Collection of Pregnancy Information.
- For women of childbearing potential. Refer to [Appendix 4](#) for Woman of Childbearing Potential (WOCBP).
- For those absence of a variant TTR genotype, absence of radionuclide bone scintigraphy (99mTc-PYP) and presence of amyloid deposits in biopsy tissue.
- Repeat not required if there is documentation of genotyping result confirming the TTR gene mutation within 5 years of enrollment.
- TTR stabilization and TTR concentration: baseline (Day 1) sample: collect pre-dose during the clinic visit. Month 1 sample: collect pre-dose and at 3 hours (±1.5 hours) post-dose. Month 6 sample: collected at

Procedure/ Assessment	Screening	Baseline visit	Month a					
			1 (±1 wee k)	3 (Tel eph one visit ±2 wee ks)	6 (±2 week s)	9 (Tel eph one visit ±2 wee ks)	12 (±2 weeks) (or within 2 weeks after End of Treatment)	Post- treatment follow-up (28+7 days after last dose)
	Day-45 to Day 0	Day 1						

7 hours (±2.5 hours) post-dose. Month 12 sample: collect at 1 hour (±30 minutes) post-dose, or End of Treatment sample: collect at time during the clinic visit. Please refer to [Section 8.6](#) for details.

- i. Tafamidis concentrations: Month 1 tafamidis concentration sample: collect pre-dose and at 3 hours (±1.5 hours) post-dose; Month 6 tafamidis concentration sample: collect at 7 hours (±2.5 hours) post-dose; Month 12 sample: collect at 1 hour (±30 minutes) post-dose, or End of Treatment sample: collect at time during the clinic visit. Please refer to [Section 8.5](#) for details.
- j. Kansas City Cardiomyopathy Questionnaire (KCCQ) should be completed before the EQ-5D-5L.

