### Appendix 1. Data Derivation Details

#### Appendix 1.1. Definition and Use of Visit Windows in Reporting

To maximize the use of all available data, the analysis visit windows are expanded. For endpoints with post-baseline assessments at Month 1, 6 and 12 (except PK endpoints), the analysis windows are defined in below table. The study day will be calculated as: date of assessment/collection – date of the first dose + 1. If two or more visits/observations fall into the same window, the visit / observation closest to the target day should be used in the analyses. If there is a tie, the later visit should be used. Note: for ECG and Echocardiogram, the central laboratory reading data takes priority. For NT-proBNP, TNI and RBP, only the central laboratory reading data are included in analysis.

Visit Label	Target Day	Definition [Day Window] - Lower	Definition [Day Window] - Upper
-------------	------------	---------------------------------	---------------------------------

Baseline	1	Day 1 = date of first dose of study treatment taken in the study  Prior to first dose of study treatment taken in the study	
Month 1	31	16	105
Month 6	181	106	270
Month 12	361	$\geq 271$ (Note: Set upper at Day 375 for PD endpoints)	

For endpoints with post-baseline assessments only at Month 6 and 12, the analysis visit windows are defined as below.

Visit Label	Target Day	Definition [Day Window] - Lower	Definition [Day Window] - Upper
Baseline	1	Day 1 = date of first dose of study treatment taken in the study  Prior to first dose of study treatment taken in the study	
Month 6	181	91	270
Month 12	361	$\geq 271$	

For PK, tafamidis concentrations will be measured at Month 1 pre-dose and 3 hours ( $\pm 1.5$  hours) post-dose; Month 6, 7 hours ( $\pm 2.5$  hours) post-dose; Month 12, 1 hour ( $\pm 30$  minutes) post-dose. The PK sampling windows are defined in below table. The sampling time window will be calculated as: time of sample collection – time of dosing of most recent study treatment.

Visit Label	Planned Time Post Dose (hours)	Definition [Time Window] – Lower (hours)	Definition [Time Window] – Upper (hours)
Month 1	0 (Pre-dose)	Prior to dosing of study treatment on the sample collection day	
Month 1	3	1.5	4.5
Month 6	7	4.5	9.5
Month 12	1	0.5	1.5

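### Protocol 6.1.1 lets the Month 6 dose be taken the previous afternoon or evening to meet a 7 h (±2.5 h) sample, but afternoon and most evening doses cannot meet that window at a daytime visit, and the SAP has no rule for the late samples

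*Protocol*

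**What the plan says.** Protocol 6.1.1 asks for the Month 6 dose to be taken 7 h (±2.5 h) before the PK sample. Note i to the Schedule of Activities (Protocol 1.3) agrees: "Month 6 tafamidis concentration sample: collect at 7 hours (±2.5 hours) post-dose". Note h sets the same timing for the paired TTR sample.

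The same part of 6.1.1 lets the home dose be taken "either in afternoon or evening of the day prior to this visit day, or in AM of this visit day". The earlier option is there to serve the sampling schedule. It applies "when the timing of PK sample collection is prohibitive for adherence with AM dosing", and the dose may be taken "in the afternoon or evening on the day prior to Month 6 visit if necessary to adhere to the PK sampling schedule". No clock limit is placed on the previous-day dose.

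SAP Appendix 1.1 calculates elapsed time as "time of sample collection – time of dosing of most recent study treatment" and gives Month 6 a single row: planned 7 h, lower limit 4.5 h, upper limit 9.5 h. SAP 6.2.2 summarizes concentrations by visit and nominal time. Neither document says what happens to a Month 6 concentration drawn outside those limits.

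**The concern.** The protocol names the previous afternoon or evening as a way to comply with a window that closes 9.5 h after the dose. Clinic visits normally take place in the daytime, so most of the dosing times named lead to a sample drawn too late. A site could offer an afternoon dose because the text lists it and still miss the window.

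Plasma tafamidis concentration at Month 6 is part of a secondary endpoint and rests on one sample per participant. The SAP widens its visit windows for other endpoints to make use of available data, but PK is excepted and has its own hour-based limits. A sample drawn at, say, 14 h fits no row of the PK table. The programmer would have to choose between leaving it out and reporting it under the 7 h heading. The first thins the Month 6 summary, and the second mixes later post-dose times into it.

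**Working it through.** **Inputs from the documents**
- Target and tolerance: 7 h ± 2.5 h (Protocol 6.1.1; Schedule of Activities notes h and i).
- Reference dose: the most recent one (SAP Appendix 1.1).
- Dosing times named: previous afternoon, previous evening, or morning of the visit day (Protocol 6.1.1).

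**Assumptions, because the documents do not give them**
- Draw times on the visit day: 07:00 to 14:00 shown.
- Afternoon is 12:00 to 18:00 and evening is 18:00 to 24:00.

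**Step 1. Reproduce the SAP window.** 7 − 2.5 = 4.5 h and 7 + 2.5 = 9.5 h. This matches Appendix 1.1.

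**Step 2. The part that needs no clinic hours.** The window closes at dose time + 9.5 h. Setting that equal to midnight gives 24:00 − 9.5 h = 14:30. A dose before 14:30 on the previous day is out of window before the visit day begins.

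**Step 3. Latest in-window draw for later doses (dose time + 9.5 h).**
- 15:00 dose: 00:30
- 18:00 dose: 03:30
- 20:00 dose: 05:30
- 22:00 dose: 07:30
- 23:00 dose: 08:30
- 23:30 dose: 09:00

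The rest of the afternoon, 14:30 to 18:00, would therefore need a draw between midnight and 03:30.

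**Step 4. Work back from the draw.** The dose must fall between draw time − 9.5 h and draw time − 4.5 h.

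| Draw on visit day | Dose must fall between | Part of previous evening (18:00–24:00) that works |
|---|---|---|
| 07:00 | 21:30 and 02:30 | 2.5 h of 6 h |
| 08:00 | 22:30 and 03:30 | 1.5 h of 6 h |
| 08:30 | 23:00 and 04:00 | 1.0 h of 6 h |
| 09:00 | 23:30 and 04:30 | 0.5 h of 6 h |
| 09:30 | 00:00 and 05:00 | none |
| 10:00 | 00:30 and 05:30 | none |
| 12:00 | 02:30 and 07:30 | none |
| 14:00 | 04:30 and 09:30 | none |

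**Step 5. How late the samples would be.** For an 08:00 draw, doses at 12:00, 15:00, 18:00, 20:00 and 22:00 the day before give 20, 17, 14, 12 and 10 h, all above 9.5 h. Doses at 22:30 and 23:00 give 9.5 and 9.0 h, both inside.

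**Step 6. Where a late sample goes in the analysis.** The only Month 6 row in the PK table is 4.5 to 9.5 h, and 6.2.2 reports by nominal time, so a 14 h sample is unassigned. The paired TTR sample departs from note h, but the SAP places Month 6 PD values by study day (Day 106 to Day 270). It therefore stays in the Month 6 PD analysis.

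**The case against.** The best defence is that the permission is conditional and the window governs. Section 6.1.1 restates the 7 h target and gives sites a scheduling rule that begins "Visit scheduling and dosing time instructions for participants must consider that the tafamidis concentration sample". The earlier dose is allowed only where it is needed to meet the sampling schedule, so a 15:00 dose for a next-day draw arguably never satisfies the condition. The permission also has a real use. An 08:00 draw needs a dose between 22:30 and 03:30, which ordinary morning dosing cannot supply, so late evening is a practical way to comply. Participants with midday or afternoon draws can use the visit-day morning dose.

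The practical use stands, and it rules out one inference a reader might draw, that no previous-day dose can ever meet the window. A dose from about 21:30 to midnight works for draws from 07:00 to just before 09:30.

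The conditional wording does not remove the conflict. The text lists the afternoon as a means of compliance and gives no clock limit, and no afternoon dose fits a daytime draw. Telling sites to consider the 7 h target while naming times that cannot meet it leaves them to find the conflict themselves.

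**Conclusion.** Protocol 6.1.1 conflicts with its own sampling figure and with SAP Appendix 1.1. Doses before 14:30 on the previous day fail at any hour of the visit day, whatever the clinic hours. The wider statement, that all afternoon doses and most evening doses fail at a daytime visit, rests on assumed draw times of 07:00 or later. Even at 07:00 only 2.5 of the 6 evening hours work, and from 09:30 no dose before midnight does.

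Three stronger readings are not supported:
- **Participants lose their Month 6 PK value.** No rule excludes out-of-window concentrations. The PK set needs only one quantifiable concentration, actual dosing and sampling times are recorded, and the optional population PK analysis could use the sample. The defect is the missing handling rule.
- **TTR data are lost.** The Month 6 PD window is in days.
- **A count of affected participants.** The documents do not say how many will use the permission, so no number can be given.

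This concerns one time point of one descriptive secondary endpoint in an estimation study. The Month 1 and Month 12 doses are taken in the clinic and are unaffected. The correction is worth making because it is cheap and the present text is inconsistent.

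**What to change.** 1. **Protocol.** Reconcile the Month 6 dosing text in 6.1.1 with notes h and i of the Schedule of Activities and with SAP Appendix 1.1, so that the dosing times the protocol names can meet the sampling window. Carry the same wording into the dosing diary instructions. Which dosing times to name is for the sponsor's clinical team.
2. **SAP.** Before database lock, state in Appendix 1.1 and 6.2.2 that Month 6 concentrations outside 4.5 to 9.5 h are summarized separately by actual elapsed time, and are neither dropped nor pooled with the 7 h values. This remains useful even if Month 6 visits are already complete.

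The cost is a wording change and one extra row in the PK table. No new samples or visits are needed.

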## 6.2. Preparation/Handling/Storage/Accountability

1. The investigator or designee must confirm appropriate temperature conditions have been maintained during transit for all study interventions received and any discrepancies are reported and resolved before use of the study intervention, as applicable for temperature-monitored shipments.
2. Only participants enrolled in the study may receive study intervention and only authorized site staff may supply or administer study intervention. All study interventions must be stored in a secure, environmentally controlled, and monitored (manual or automated recording) area in accordance with the labeled storage conditions with access limited to the investigator and authorized site staff. At a minimum, daily minimum and maximum temperatures for all site storage locations must be documented and available upon request. Data for nonworking days must indicate the minimum and maximum temperature since previously documented for all site storage locations upon return to business.
3. The investigator, institution, or the head of the medical institution (where applicable) is responsible for study intervention accountability, reconciliation, and record maintenance (ie, receipt, reconciliation, and final disposition records). All study interventions will be accounted for using an investigational product accountability form/record. At each scheduled clinic visits starting at Month 1; participants will bring their study medication with them to the site. The investigator's site must maintain adequate records documenting the receipt, use, loss, or other disposition of the drug supplies as outlined in the monitoring plan.
4. Further guidance and information for the final disposition of unused study interventions are provided in the package insert.
5. Any storage conditions stated in the SRSD will be superseded by the storage conditions stated on the product label.
6. Study interventions should be stored in their original containers and in accordance with the labels.
7. Site staff will instruct participants on the proper storage requirements for take-home study intervention.
8. Any excursions from the study intervention label storage conditions should be reported to Pfizer upon discovery along with any actions taken. The site should actively pursue options for returning the study intervention to the storage conditions described in the labeling, as soon as possible. Once an excursion is identified, the study intervention must be quarantined and not used until Pfizer provides permission to use the study intervention. It will not be considered a protocol deviation if Pfizer

PFIZER CONFIDENTIAL

approves the use of the study intervention after the temperature excursion. Use of the study intervention prior to Pfizer approval will be considered a protocol deviation. Specific details regarding the definition of an excursion and information the site should report for each excursion will be provided to the site in the package insert.

9. The sponsor or designee will provide guidance on the destruction of unused study intervention (eg, at the site). If destruction is authorized to take place at the investigator site, the investigator must ensure that the materials are destroyed in compliance with applicable environmental regulations, institutional policy, and any special instructions provided by Pfizer, and all destruction must be adequately documented.

#### **6.2.1. Preparation and Dispensing**

See the package insert for instructions on how to prepare the investigational product for administration. Investigational product should be prepared and dispensed by an appropriately qualified and experienced member of the study staff (eg, physician, nurse, physician's assistant, nurse practitioner, pharmacy assistant/technician, or pharmacist) as allowed by local, state, and institutional guidance.

### **6.3. Measures to Minimize Bias: Randomization and Blinding**

#### **6.3.1. Allocation to Investigational Product**

This is a single-arm study. Participant eligibility for participation in the study will receive tafamidis 61 mg, the approved dose in China, once daily for 12 months following the assessments at the screening and baseline visits.

There is no requirement of blinding and randomization.

### **6.4. Study Intervention Compliance**

Participants will be instructed to take the medication on a daily basis. They will also be instructed to bring all of their study medication back to the study site, including used and unused study medication, at each scheduled study visit so that the total amount of drug taken can be determined and unused medication collected by site personnel.

Participant compliance with investigational product will be assessed at each visit. Compliance will be assessed by counting returned capsules. Participants will be considered to be adherent to the dosing requirements of the study if they have taken study medication per day on at least 80% of the days of study participation. Deviation(s) from the prescribed dosage regimen should be recorded in the CRF. Participants with less than 80% dosing adherence will be excluded from the per protocol analysis set.

All doses of investigational product will be administered by the appropriately designated study staff at the investigator site.

